5.1 General

A randomized, single-blinded, parallel study, in which each subject will undergo one catheterization comprising of 6 cycles of filling and emptying the bladder. Each cycle will comprise of filling the bladder with 250mL of saline liquid (50mL/min) through the catheter, followed by bladder emptying through the catheter. The catheter will be rotated during emptying at each occurrence of a flow-stop to release any mucosal suction, with the MHC or 2EC, depending on randomization. To ensure that all catheters are rotated at some point during drainage, every catheter should be rotated after complete emptying. Subjects shall be sitting or standing for the catheterization and filling/emptying cycles to increase the efficiency of drainage.

Upon first insertion of the catheter, the residual volume pre-catheterization will be recorded to ensure minimal residual urine left in the bladder prior to the 6 cycles.

The effect of the micro-hole zone or conventional eyelets on the epithelial and vascular urothelial tissue will be assessed with cystoscopies before and after the catheterization including 6 cycles of filling/emptying/rotating.

One investigator will perform the cystoscopies, catheterizations, and make initial assessments of the cystoscopy images according to a 4-point rating scale as described in 5.3. Two additional investigators will evaluate the endoscopic images post-procedure in a blinded fashion. The evaluations by the 3 investigators will be compared.

The urine at pre- and post-catheterization at Visit 2will be collected for each subject, the total volume noted, and the container will be sent to a local lab for examination of microscopic RBC[1] and WBC results.

Each visit will take approximately 1-2 hours to complete.

Figure 5-1 presents the study overview and Table 7-1 presents the schedule of assessments.

[figure not shown]

Figure 5-1 Study overview

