5.7 Blinding

Subjects will not be blinded during this investigation, as it is not possible to blind the products due to visible differences. The two investigators conducting the cystoscopy reviews will be blinded. The images will be deidentified and uploaded to a secure site. The images will be identified with a subject number, date, and time. The investigators will be provided access to the secure site for their review. Each investigator will grade both the post-catheterization image and pre-catheterization image, i.e., from the same location (grading is done in a comparative manner).

Any discordant gradings will be adjudicated amongst the investigators.

Additionally, the trial statistician will be blinded until database lock to ensure decisions related to data before database lock do not affect final results.

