20.7 Investigator's reporting responsibilities

PI at each site must assess all (S)AE's that occur at his/her site.

All serious adverse events and serious adverse device effects must be reported to sponsor within 24 hours of the site becoming aware of the event.

A device deficiency that could have led to a serious adverse event but did not because suitable action was taken, intervention had been made or because of fortunate circumstances should be reported to sponsor within 24 hours of the site becoming aware of the event.

New findings and/or updates in relation to already reported serious events should also be reported to sponsor within 24 hours of the site becoming aware of the event.

Device deficiencies and all adverse device effects must be reported to sponsor within 10 days of becoming aware of the event.

When reporting the SAE, the relationship to the test material shall be described whether the event is considered:

- Not related, the event has no temporal relationship with the use of the test material or the procedures.
- Unlikely related, the relationship with the use of the test material seems not relevant and/or the event can be reasonably explained by another cause, but additional information may be obtained.
- Possibly related, the relationship with the use of the test material is weak but cannot be ruled out
 completely. Alternative causes are also possible (e.g., an underlying or concurrent illness/ clinical
 condition or/and an effect of another device, drug, or treatment). Cases where relatedness cannot be
 assessed, or no information has been obtained should also be classified as possible.
- **Probably related**, the relationship with the use of the test material seems relevant and/or the event cannot reasonably be explained by another cause, but additional information may be obtained.
- **Definitely related/Causal relationship,** the event has a temporal relationship with the test material use/application or procedures.

The investigator will assess intensity for each AE and SAE reported during the investigation and assign it to one of the following categories:

- Mild, the intensity of the event is mild with no further action or intervention
- Moderate, the intensity of the event will lead to an action or intervention to solve the event
- Severe, the intensity of the event will lead to follow up on the action or intervention, as the effect of the action or intervention may not decrease the symptoms.

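### Section 20.7 grades adverse event intensity partly by how the event was managed, so the three categories leave gaps, overlap, and do not rank events by intensity (minor)

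*Combined protocol and SAP*

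**What the plan says.** The grade is mandatory. Section 20.7 states: "The investigator will assess intensity for each AE and SAE reported during the investigation and assign it to one of the following categories". The three definitions are:

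- The lowest grade carries two conditions, one on intensity and one on management: "Mild, the intensity of the event is mild with no further action or intervention"
- The middle grade is worded by management only: "Moderate, the intensity of the event will lead to an action or intervention to solve the event"
- The highest grade is worded by what comes after the management: "Severe, the intensity of the event will lead to follow up on the action or intervention". The reason given is that the remedy might not relieve the symptoms.

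The plan contains no other intensity scale.

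On who grades, section 20.7 adds: "PI at each site must assess all (S)AE's that occur at his/her site". Section 5.1 says: "One investigator will perform the cystoscopies, catheterizations, and make initial assessments of the cystoscopy images". Section 5.7 leaves subjects unblinded, "as it is not possible to blind the products due to visible differences", and names only the two image reviewers and, until database lock, the statistician as blinded.

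On output, section 10 promises that adverse events will appear in a listing, a summary or both, and that summaries are shown by treatment. Section 10.1 bases the adverse event summary on the safety population. No tabulation by intensity is named.

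**The concern.** How intense an event is and what was done about it are different attributes. A short, intense event may need nothing done, and a trivial one may be given a remedy. A scale that reads intensity from management cannot separate these cases.

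Two things are at stake. First, the grade may not measure what it is named for. Each subject has one catheterisation with six filling and emptying cycles, and follow-up ends at Visit 2 (sections 5.1 and 7.3). Brief procedural events that end without intervention are therefore plausible, although the plan gives no expected event profile. Apart from events that are intrinsically mild, such events have no grade.

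Second, the decision to act belongs to the site. If the person deciding knows the catheter, a difference in grades between arms could come from a difference in readiness to act.

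**Working it through.** The plan states no figure for intensity, so there is nothing to reproduce. The check applies the section 20.7 wording to every combination of intrinsic intensity and management.

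Conditions taken from the text:

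- Mild: intensity is mild **and** no action.
- Moderate: the event leads to an action; no condition on intensity.
- Severe: the action is followed up; no separate condition on intensity.

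| Intrinsic intensity | No action | Action only | Action plus follow-up |
|---|---|---|---|
| Mild | Mild | Moderate | Moderate and Severe |
| Moderate | none fits | Moderate | Moderate and Severe |
| Severe | none fits | Moderate | Moderate and Severe |

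Count: 1 (Mild) + 2 (no category) + 3 (Moderate only) + 3 (both Moderate and Severe) = 9.

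Three results follow.

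1. The scale is not exhaustive: 2 of 9 combinations have no category.
2. It is not mutually exclusive: 3 of 9 meet two definitions, and section 20.7 gives no rule for choosing between them.
3. Once any action is taken, intensity no longer affects the grade. Within the second and third columns all three rows are identical.

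These are counts of logical combinations, not of expected events. The plan gives no adverse event or intervention rate, so the share of events misgraded cannot be calculated.

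On knowledge of the arm, the steps are: one investigator performs the catheterisations (5.1); the products look different (5.7); the blinded roles named are the image reviewers and the statistician (5.7); the principal investigator assesses all events (20.7). The plan never says in words that the person grading events is unblinded. It is a strong inference, not a stated fact.

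On what depends on the grade: serious events are identified by outcome criteria in section 20.4. The reporting deadlines in sections 20.7 and 20.8 follow seriousness, device deficiency or device relatedness. Medical Advisor review in section 20.9 follows seriousness, device deficiency and relatedness. The primary endpoint in section 5.2.1 is a cystoscopic grading. None of these uses intensity.

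**The case against.** The best defence is that this is a descriptive attribute in an exploratory study planned for 40 completers, with no pass/fail criterion (section 10.6) and no decision tied to intensity. That stands, and it sets the priority.

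A second defence is that the text speaks of the intensity leading to an action, so action is meant as a marker of intensity, and that a reader would apply the highest category that fits. The highest-category convention would remove the overlap, but it is not written down. It would not fill the two empty cells, and it would grade an intrinsically mild event with follow-up as Severe.

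A third is that new definitions would not blind the grader, and that interference with usual activity suits poorly an event during a clinic procedure of one to two hours. Both points are fair. The first limits what the fix can achieve, and the second shapes its wording.

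Three stronger readings are tempting, and the documents do not support them.

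- A reader might infer that severe untreated events must be graded Mild. They need not be: Mild also requires mild intensity, so such an event has no category. An investigator obliged to choose might default to Mild, but the text does not direct it.
- A reader might infer that a planned severity table will be biased. No such table is specified. The concern applies to whatever listing or summary of intensity is produced.
- A reader might want a figure for the resulting difference between arms. The plan offers no rates from which to derive one, and any example would be invented.

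**Conclusion.** The point holds as a defect in a stated rule. Section 20.7 mixes intensity with management; its categories are neither exhaustive nor mutually exclusive, and they grade a trivial event that is acted on as Moderate. By wording alone, 2 of 9 intensity-by-management combinations are unclassifiable and 3 of 9 meet two definitions.

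Any presentation of intensity by arm would partly describe intervention decisions. That part of the conclusion rests on the inference that the grading investigator knows the arm, which is very likely but not stated. The practical effect is limited to descriptive safety data and cannot be quantified from the documents. Priority: minor.

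**What to change.** In section 20.7, replace the three definitions with ones based on the subject's symptoms and their tolerability or functional interference, assigned regardless of whether anything was done. For example:

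- Mild: noticed but easily tolerated.
- Moderate: clearly uncomfortable, or interferes with what the subject is doing, including staying in position for the filling and emptying cycles.
- Severe: intolerable, or prevents the activity.

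This wording also suits brief events during the procedure. Because section 20.1 counts abnormal laboratory findings as adverse events, add one sentence on grading findings without symptoms.

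Record action taken and follow-up needed as two separate fields on the adverse event form, if they are not there already; the form is not among the documents. Nothing now captured is then lost.

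The cost is three definitions and minor form edits, with no added visit and no change to any treatment decision. The remaining limitation is that the grade is still a judgement by an investigator who is probably aware of the arm, and the clinical investigation report should say so wherever intensity is shown by arm.

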20.8 Sponsors Reporting Responsibilities

It is the responsibility of sponsor to ensure that the following are reported to national regulatory authorities immediately, but no later than 7 calendar days following the date of awareness by sponsor.

All serious adverse events.

All serious device effects.

All device deficiencies that could have led to serious adverse events but did not because suitable action was taken, intervention had been made or because of fortunate circumstances.

New findings and/or updates in relation to already reported events.

If the serious adverse event results in imminent risk of death, serious injury, or serious illness that requires prompt remedial action for other subjects, users or other persons or a new finding to such a serious adverse event, sponsor must immediately but no later than 2 calendar days after awareness by sponsor report the event to national regulatory authorities and ethics committees, as applicable.

It is the responsibility of sponsor to inform all investigators in writing within 10 working days if device deficiencies, adverse events, adverse device effects, near-incidents, serious adverse events, serious adverse device effects or unanticipated serious adverse device effects lead to corrective actions (e.g., change of IFU).

20.9 Medical Advisor Safety Review

The Sponsor is responsible for ensuring all Serious Adverse Event (s) are provided to the Medical Advisor for review and discussion.

The Medical Advisor will be informed of the following:

- All serious adverse events related to the investigation product or clinical investigation and serious adverse device effects
- A device deficiency that could have led to a serious adverse event but did not because suitable action
 was taken, intervention had been made or because of fortunate circumstances
- New findings and/or updates in relation to already reported serious events

In addition, the Medical Advisor will receive lists of any reported AE's and ADE's related to the investigation product or clinical investigation, as defined by sponsor for a review of safety.

Correspondence, decisions, and recommendations regarding safety in the Clinical Investigation from the Medical Advisor must be documented and saved electronically in the Sponsor File.

20.10 Data Safety and Monitoring Board (DSMB)

The review of all safety data will be conducted on an ongoing basis to identify any potential safety issues. If needed, the Medical Advisor can call for a Data Safety and Monitoring Board meeting with relevant members, to discuss potential safety issues and further recommendations, if relevant.

Based on the safety data review, the Medical Advisor along with the DSMB may recommend that the sponsor modifies, temporarily suspends, or terminates the clinical investigation.

Correspondence, decisions, and recommendations regarding safety in the Clinical Investigation from the Data Safety and Monitoring Board must be documented in meeting minutes and saved electronically in the Sponsor File.

All final decisions, however, regarding clinical investigation modifications, remain with the Sponsor.

21 Suspension or premature termination of the clinical investigation

Sponsor may suspend or prematurely terminate an investigation site or the entire clinical investigation for documented significant reasons.

If a suspicion of an unacceptable risk to subjects develops during the clinical investigation, sponsor will suspend the investigation while the risk is assessed. Sponsor will terminate the investigation if an unacceptable risk is confirmed. Sponsor will ensure that the premature termination will be justified in writing and will promptly inform the IRB. If monitoring or auditing of the clinical investigation identifies serious or repeated deviations, sponsor will suspend or terminate the particular investigation site. The sponsor or investigator will inform the IRB about the termination of the site.

If suspension or termination of the clinical investigation occurs, the investigator(s) will promptly inform the enrolled subjects. Sponsor will provide resources to fulfil the obligations from the CIP for follow-up of the subjects, as necessary.

22 Clinical investigation report

At completion of the investigation sponsor is responsible for writing the clinical investigation report. The report is retained on file. The report contains a critical evaluation of all data, which have been collected during the investigation. The report describes the methodology and design and a data analysis, including statistical preparation and conclusion.

Sponsor and national coordinating investigators must sign the final version of the clinical investigation report or an affidavit, indicating their agreement with the contents. If no coordinating investigators are appointed, then the signatures of the principal investigators should be obtained.

The clinical investigation report must be submitted to IRB.

23 "Publication policy

The results of the investigation, positive as well as negative, may be communicated by abstracts, posters, or oral presentations provided that opportunity is given for sponsor to discuss the contents and any conclusions drawn, before the abstract, paper, or visual presentations are finalised. In all cases the subject's identity will remain confidential.

Sponsor will undertake to comment on the draft documents within 30 working days of receipt, but the final decision on the contents and format of the publication from the conclusions drawn, will remain with the authors.

No preliminary results will be published (if sub studies are performed using an umbrella CIP, results and conclusions for each sub investigation can be published).

Data from the investigation is considered confidential until it is published according to the conditions of this CIP.

Sponsor may publish single subject case stories at any time during and after the investigation.

Sponsor reserves the right to use the data (published and unpublished) for reimbursement or regulatory purposes.

24 Suspension/termination of the clinical investigation

Sponsor will withdraw from sponsorship of the clinical investigation if:

- major non-adherence to the clinical investigation plan is occurring;
- it is anticipated that the subject recruitment will not be adequate to meet the investigation objectives [at least 75%] of the subjects should be entered within the recruitment time.

In case sponsor withdraws, sponsorship for the subjects already recruited into the clinical investigation will continue.

25 References

